Participants are free to withdraw from participation in the study at any time upon request. Under certain circumstances, an individual participant may be terminated from participation in this study. Specific events that will result in early termination include:

- Participant refuses further participation
- Participant relocates prior to completion of the biopsy visit
- If any laboratory abnormality, or other medical condition or situation occurs such that continued participation in the study would not be in the best interest of the participant
- If the participant meets an exclusion criterion (either newly developed or not previously recognized) that precludes further study participation

The reason for participant discontinuation or withdrawal from the study will be recorded on the appropriate Case Report Form (CRF).

15. Risks to Participants

Rectal Biopsies

For this proposed work, there are some risks. Risks associated with lower gastrointestinal endoscopy performed for clinical purposes include colitis from chemicals for endoscope sterilization, bowel perforation, bleeding, diverticulitis, and infection. A delegated, licensed medical professional whom the PI has trained in the procedure will complete all biopsies. To minimize risks, rigid proctoscopy, rather than flexible sigmoidoscopy or colonoscopy, will be used in this study and the number of biopsies taken will be limited to 12. Colonoscopy has been shown to be associated with a still low, but significantly greater risk of complications than rectosigmoidoscopy¹⁰. The frequency of serious complications after flexible sigmoidoscopy is extremely low and complications from rigid sigmoidoscopy are presumably even lower, but

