Acquisition of HIV drug resistance is a theoretic concern for HIV positive people taking intermittent dosing of anti-HIV medication. For this protocol, study staff will test participants for HIV at study entry and monitor clinically for high-risk behavior or any signs of acute HIV infection at study visits. If high-risk behavior (e.g. unprotected anal intercourse with a man of unknown HIV status) or symptoms of acute HIV infection are reported, and HIV antibody test will be repeated, and the participant will be counseled about the need for any follow-up testing. Clinical signs and symptoms of acute HIV infection that will be queried include: fever, fatigue, malaise, skin rash, swollen glands, oral/genital ulcers, myalgia/arthralgia. [name] will review all reports of clinical signs/symptoms to determine appropriate follow-up and linkage to care as necessary. If a diagnosis of acute HIV infection is thought to be possible or determined by

repeat HIV testing, the participant will be discontinued from the study. For this protocol, study staff will test participants for HIV at study entry and monitor clinically for high-risk behavior or any signs of acute HIV infection at study visits.

Participants will be asked to abstain from receptive anal or vaginal sex from the time they take the study drug to 7 days after the biopsy procedure is completed in order to limit additional exposures (e.g. semen, douching, additional lubricants) to the rectal or vaginal mucosa.

Participants taking Biktarvy® will be counseled that they should not expect to achieve protection from HIV infection by taking drug during this study, as they will be provided a limited supply. All participants included in the study that have an interest in taking PrEP for HIV prevention, will be referred to an area PrEP provider at the termination of the study. The Hope Clinic has compiled a resource sheet of area providers that will be distributed to interested participants.

Blood Sample Risks

The most common risks of blood sample collection are pain at the puncture site, bruising, and a feeling of lightheadedness. To minimize these risks, blood draws will be performed by trained personnel, and will be performed in a secure environment with access to first aid equipment, bandages, and trained healthcare professionals.

16. Potential Benefits to Participants

Subjects are not expected to derive direct benefit from this study.

17. Compensation to Participants

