Primary Outcomes: Comparison of doxycycline concentrations in blood and tissue between men and women. Plasma doxycycline concentrations at 24 hours will be compared between men and women using a Wilcoxon test. Median rectal and vaginal swab doxycycline concentrations collected at 24 hours after dosing will be compared using a Wilcoxon test. Median rectal and cervical tissues doxycycline concentrations collected at 24 hours after dosing will be compared using a Wilcoxon test. P-values less than 0.05 will be considered significant.

Exploratory Outcomes: Comparison of TAF, FTC, and BIC concentrations in blood and tissue between men and women. Plasma TAF, FTC, and BIC concentrations at 24 hours will be compared between men and women using a Wilcoxon test. Median rectal and vaginal swab TAF, FTC, and BIC concentrations collected at 24 hours after dosing will be compared using a Wilcoxon test. Median rectal and cervical tissue TAF, FTC, and BIC concentrations collected at 24 hours after dosing will be compared using a Wilcoxon test. P-values less than 0.05 will be considered significant.

19. Provisions to Monitor the Data to Ensure the Safety of Participants

Adverse Events

An Adverse Event (AE) as any untoward medical occurrence in a clinical investigation subject administered a pharmaceutical product regardless of its causal relationship to the study treatment. An AE can therefore be any unfavorable and unintended sign (including an abnormal laboratory finding), symptom or disease temporally associated with the use of a medicinal (investigational) product.

Any AE that is reported to either the investigators or their designated research associates by a study subject or by medical staff caring for the subject and which meets the criteria will be documented in the participant's chart. The reporting period for participant AEs begins at enrollment (Visit 2) and continues until the subject either completes or withdraws from the study.

All AEs and laboratory abnormalities will be graded according to the Division of AIDS Table for Grading the Severity of Adult and Pediatric Adverse Events (DAIDS AE Grading Table), Version

2.1, July 2017, which can be found on the DAIDS RCC Web site: http://rcc.tech-res.com/tox_tables.htm.

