7. Important medical events/experiences that may not result in death, be life threatening, or require hospitalization may be considered a serious adverse event/experience when, based upon appropriate medical judgment, they may jeopardize the subject and may require medical or surgical intervention to prevent one of the outcomes listed above, i.e., death, a life-threatening adverse event/experience, inpatient hospitalization or prolongation of existing hospitalization, a persistent or significant disability/incapacity, or a congenital anomaly/birth defect. Examples of such medical events/experiences include allergic bronchospasm requiring intensive treatment in an emergency room or at home, blood dyscrasias or convulsions that do not result in inpatient hospitalization, or the development of drug dependency or drug abuse.

In this protocol, spontaneous and elective abortions will be also be considered SAEs.

The reporting period for participant SAEs begins at enrollment (Visit 2) and continues until the subject either completes or withdraws from the study. All SAEs will be reported to the Medical Monitor within 24 hours of site awareness and reported to the IRB per its policies.

It should however be noted that a severe adverse event /experience is not necessarily serious, as the term severe is a measure of intensity while a serious adverse event (SAE) is determined based on the aforementioned regulatory criteria.

Data Safety Monitoring

AEs ≥ Grade 3 or 4 and targeted AEs will be reviewed in real time by study investigators.

Medical Monitor

A medical monitor will be assigned to this study for the purpose of safety oversight. The medical monitor will be notified of all SAEs within 24 hours of site awareness and receive quarterly summary reports of all AEs meeting the previously described criteria.

20. Provisions to Protect the Privacy Interests of Participants

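### AE and SAE reporting ends at completion or withdrawal, so a dosed participant who is stopped early has no assured safety reporting to day 7 (minor)

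*Combined protocol and SAP*

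**What the plan says.** Section 19 (Adverse Events): "The reporting period for participant AEs begins at enrollment (Visit 2) and continues until the subject either completes or withdraws from the study". The sentence for SAEs in the same section has the same start and end.

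The protocol also takes some participants off study after dosing:

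- **Acute HIV** (Section 15, Biktarvy): the rule closes with "repeat HIV testing, the participant will be discontinued from the study"; its condition opens with "If a diagnosis of acute HIV infection is thought to be possible or determined by". The signs to be asked about are "fever, fatigue, malaise, skin rash, swollen glands, oral/genital ulcers, myalgia/arthralgia". A designated member of the team "will review all reports of clinical signs/symptoms to determine appropriate follow-up and linkage to care as necessary".
- **Pregnancy** (Section 15, Doxycycline): a woman who becomes pregnant is removed.
- **Other stops** (Section 14, headed Withdrawal of Participants): "Specific events that will result in early termination include" a medical condition that makes staying on study unwise, and an exclusion criterion that is newly met or newly recognised.

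On what happens next, Section 14 says "The reason for participant discontinuation or withdrawal from the study will be recorded" on the case report form. It describes no early-termination visit and no safety contact after the stop.

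Each participant takes one dose of each drug, about 1 h before Visit 2 (Section 6). The last scheduled visit is Visit 10, 7 days after the dose.

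**The concern.** In a multiple-dose trial, a stop usually ends drug exposure, and it can be natural for follow-up to end soon after. Here the whole exposure has occurred before the reporting window opens. A later stop spares the remaining procedures, including the biopsy if it comes before Visit 6, but it removes no drug. The participant carries the same drug risk as one who stays to Visit 10, yet may have a much shorter reporting period.

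Those stopped are also not a random subset. They are stopped because of symptoms, a new condition or a pregnancy, so they are the people for whom reporting to day 7 matters most. Pregnancy shows the conflict within the protocol most clearly. Section 19 counts abortions and congenital anomalies as SAEs, while Section 15 removes the woman, and removal may end the period in which an SAE is reportable.

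**Working it through.** The plan gives no figure to reproduce. The check is on the wording and then on time.

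**Wording.** Reporting ends on withdrawal, but the acute-HIV rule speaks of discontinuation and the pregnancy rule of removal. Two readings are possible.

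1. Withdrawal includes stops directed by staff. The heading of Section 14, which covers early termination, supports this. Reporting then closes at the stop.
2. Withdrawal means the participant's own decision only. Section 14 supports this where it names discontinuation and withdrawal as alternatives. Reporting for a discontinued participant then has no stated end.

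Neither reading gives staff a rule that carries reporting to day 7.

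**Time at risk.** Inputs are the nominal visit times in Section 6 and Table 1: Visit 2 at 1 h, Visit 5 at 8 h, Visits 6 to 9 at 24, 48, 72 and 96 h, and Visit 10 at 7 × 24 = 168 h.

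Full window = 168 − 1 = 167 h. For a stop just after a visit at hour t, reporting time that can be closed = 168 − t, and its share = (168 − t)/167.

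| Stop just after | t (h) | 168 − t (h) | Days | Share |
|---|---|---|---|---|
| Visit 2 | 1 | 167 | 6.96 | 100% |
| Visit 5 | 8 | 160 | 6.67 | 95.8% |
| Visit 6 | 24 | 144 | 6.00 | 86.2% |
| Visit 7 | 48 | 120 | 5.00 | 71.9% |
| Visit 8 | 72 | 96 | 4.00 | 57.5% |
| Visit 9 | 96 | 72 | 3.00 | 43.1% |

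**What the post-biopsy contact recovers.** Section 6 provides a contact 24 to 48 h after the biopsy, or at the next visit if sooner. It reaches biopsy donors only and asks about procedure-related problems. For a donor stopped between Visits 6 and 7 it falls at 24 + 24 = 48 h to 24 + 48 = 72 h after the dose. That leaves 168 − 48 = 120 h (5 days) to 168 − 72 = 96 h (4 days) with no stated AE contact. For a stop after Visit 7 the contact has already taken place. For a stop before Visit 6 there is none, because there was no biopsy.

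**Pregnancy.** Sections 1 and 6 place a test at the biopsy visit, which is after the dose. (Table 1 as extracted shows the mark under Visit 7, which would make the remaining time 5 days instead of 6.) A woman found pregnant at Visit 6 has no vaginal or cervical biopsy, so the donor contact does not reach her on that account.

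**Effect on the SAP.** All comparisons are at 24 h. A stop after Visit 6 leaves those samples in hand. One loss before Visit 6 changes 10 v 10 to 9 v 10.

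**The case against.** The best defence is that the text never says reporting ends on discontinuation, and that other safeguards exist. Section 15 provides counselling and linkage to care for possible acute HIV, and tells women who had biopsies to call if problems persist. Section 6 allows extra visits when needed. Section 19 sends SAEs to the IRB under policies that we cannot see. The drugs are approved and given once to about 20 people.

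The first part stands: that a staff-directed stop closes reporting is an inference, and the alternative is an undefined end. The safeguards are real, but they are clinical care, optional, or dependent on the participant calling. None extends the reporting period.

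Several stronger readings are tempting, and the documents do not support them.

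- *A rash that leads to a stop goes unreported.* Section 15 stops no one for a rash alone; reported symptoms lead to a repeat test and counselling. A rash present at the stop arose inside the window, so it is charted, graded and assessed for relatedness. Only later worsening could be missed.
- *Participants are stopped on mere suspicion of HIV.* The sentence can be read so, but repeat testing may govern both halves of it. The point here does not depend on which is meant.
- *Laboratory abnormalities and relocation are further important routes.* Safety laboratory tests are named at screening only. Relocation counts only before the biopsy visit, and entry requires no plans to move for 4 months. Neither adds much.
- *Reporting to day 7 would resolve the pregnancy conflict.* It would not. A pregnant woman who stayed to Visit 10 would face the same gap, which comes from the short follow-up.

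**Conclusion.** The point holds as a minor one. The protocol stops some dosed participants early and does not assure AE/SAE reporting for them up to day 7. The time that can be closed is 144 of 167 h for a stop just after Visit 6, 160 h after Visit 5, and up to 167 h after Visit 2.

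These are upper limits per stopped participant, at nominal visit times, on the reading that a staff-directed stop counts as withdrawal. On the other reading the same hours have no stated rule. The documents give no rate of early stops, so no expected number of missed events can be calculated and none is assumed.

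A reader might infer that the primary results are threatened. They are not: the SAP tests use 24 h samples only, and early stops would barely change them.

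**What to change.** In Section 19, define the end of AE and SAE reporting as day 7 after the dose for every dosed participant, whether or not they remain on study, unless the participant refuses further contact. A phone or electronic contact is enough; no clinic visit is needed. Add a cross-reference in Section 14 so that staff who stop a participant see the rule.

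State separately that a pregnancy found after dosing will be followed to its outcome, because the abortions and congenital anomalies that Section 19 counts as SAEs cannot be captured by day 7.

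The cost is a few sentences, one or a few contacts per stopped participant, and a longer follow-up in the rare event of a pregnancy. Sampling, biopsies and the SAP analyses need no change.

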| Study Title | Multipurpose Prevention of Post-Exposure Prophylaxis Regimens (Combo-PEP) |
| Study Design | 
To determine tissue pharmacology of a single dose of doxycycline for STI PEP, investigators at Emory University will collaborate with the Centers for Disease Control and Prevention (CDC) to conduct a clinical trial of up to 20 MSM and women aged 18-59, with measurement of anti-retroviral drug and doxycycline concentrations in the rectum and vaginal regions.
 
Study staff will plan to enroll participants who are HIV negative, at low risk for HIV and are not currently (or have no current plans) taking Post Exposure Prophylaxis (PEP) or Pre- Exposure Prophylaxis (PrEP). Enrolled participants will take a single dose of doxycycline (200mg) and Biktarvy® (200mg).
 
Biological specimens will be collected at 10 time points during this study. Study staff will recruit participants through existing research databases at the Hope Clinic and the Rollins School of Public Health, Research Match, and Clinical Data Warehouse. Internet and paper advertisements and community venues will also be used. At the first study visit, eligibility will be determined and screening blood work (approximately 14 mL), including an HIV test, will be performed. Participants will receive study drug in clinic and will provide documentation of taking doses (doxycycline and Biktarvy®) of the drug at home. During all study visits, participants will undergo blood collection (approximately 14 mL or 3 teaspoons of blood will be obtained), a urine sample, and collection of vaginal and rectal secretions. At certain visits, a vaginal and cervical biopsy will be performed on women, and a rectal biopsy will be performed on men, in addition to swab procedures. Women will have the option to do a rectal biopsy, as well. A pregnancy test will be done on women of childbearing potential at their screening and biopsy visit.
 |
| Primary Objective | To determine tissue pharmacology of single dose doxycycline for STI PEP |
| Secondary Objective(s) | To determine the tissue pharmacology of single dose bictegravir for HIV PEP. |

| | |
|---|---|
| Research Intervention(s)/Interactions | Doxycycline (200mg) and Biktarvy® (200mg) one combined dose |

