affected by HIV. The majority of HIV infections among MSM occur through exposure to the rectal mucosa during condomless receptive anal intercourse (CRAI), and among women through exposure to the vaginal mucosa regions, within the female genital tract, during condomless vaginal intercourse. To aid in prevention, pre-exposure prophylaxis (PrEP) and post-exposure prophylaxis (PEP) are recommended for HIV exposure. Current CDC recommendations for PrEP is to take the combination anti-HIV drug, tenofovir+emtricitabine (TDF/FTC or TAF/FTC), on a daily basis for the duration of someone's HIV risk exposure period, which could be months or years. For PEP, a three-drug anti-HIV medication is recommended within 72 hours of a possible exposure, for a 28-day course, according to the CDC. While PrEP and PEP are efficacious, both the daily dosing of PrEP and the 28-day course of PEP limit their utility in practice, as many users find long term adherence to these regimens to be difficult. Therefore, short course regimens taken around the time of sex (On-demand or Event-Driven PrEP; ED-PrEP) are appealing to some, and WHO endorses one such ED-PrEP regimen for MSM: two doses of TDF/FTC between 2 and 24 hours before sex, one dose 24 hours after sex, and another dose 48 hours after sex. Although short course regimens have been proven to reduce one's risk of HIV infection, interventions for STI prevention have yet to be approved for use. Recent studies have shown a single dose of oral doxycycline (DOX) taken within 24 hours after having sex, can protect against STIs among MSM. A multi-purpose dosing strategy that combines DOX with ARVs could allow for a single event-driven oral dosing combination to be taken after sex for protection against HIV and other STI infections. The aim of this study is to better understand the ability of DOX, TAF, FTC, & bictegravir (BIC) to penetrate mucosal tissues after a single oral dose, and to examine how well the tissues retain protective drug levels over an extended period of time in both men and women.

4. Study Endpoints

Primary Endpoint: to compare doxycycline concentrations in rectal and vaginal biopsies collected 24 hours after a single dose.

Secondary Endpoint: The comparison of bictegravir concentrations in rectal and vaginal biopsies collected 24 hours after a single dose.

5. Study Intervention/Investigational Agent

Doxycycline

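### Section 4 and the SAP rank the endpoints differently: one biopsy endpoint becomes three unadjusted primary tests, and bictegravir drops from secondary to exploratory

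*Combined protocol and SAP*

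**What the plan says.** The study summary gives the primary objective as "To determine tissue pharmacology of single dose doxycycline for STI PEP" and the secondary objective as "To determine the tissue pharmacology of single dose bictegravir for HIV PEP".

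Section 4 (Study Endpoints) turns each into one endpoint:

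- for doxycycline, at the first rank: "Primary Endpoint: to compare doxycycline concentrations in rectal and vaginal biopsies collected 24 hours after a single dose"
- for bictegravir, at the next rank down: "Secondary Endpoint: The comparison of bictegravir concentrations in rectal and vaginal biopsies collected 24 hours after a single dose"

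Section 4 gives plasma and swab concentrations no rank.

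The Statistical Analysis Plan, placed under Section 18, has two tiers. The first opens "Primary Outcomes: Comparison of doxycycline concentrations in blood and tissue between men and women" and contains three tests:

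- plasma: "Plasma doxycycline concentrations at 24 hours will be compared between men and women using a Wilcoxon test"
- swabs: "Median rectal and vaginal swab doxycycline concentrations collected at 24 hours after dosing will be compared using a Wilcoxon test"
- tissue: a Wilcoxon test of rectal against cervical doxycycline at 24 hours.

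The second tier opens "Exploratory Outcomes: Comparison of TAF, FTC, and BIC concentrations in blood and tissue between men and women" and repeats the three tests for those drugs. In both tiers a P-value below 0.05 counts as significant. There is no secondary tier, no order of testing and no adjustment for multiple tests.

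**The concern.** Two current sections of one document disagree on what the primary result is, and nothing says which prevails. Suppose the plasma or swab test is significant and the tissue test is not. Under the SAP that is a significant primary outcome. Under Section 4 it has no bearing on the primary endpoint. The choice could then be made after the data are seen.

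Plasma is the clearest mismatch, because a comparison of blood levels between men and women does not measure tissue pharmacology.

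Bictegravir has a related problem. It carries the declared secondary objective and endpoint, but the SAP groups it with TAF and FTC at exploratory rank.

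**Working it through.** **Tiers side by side**

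| Measure at 24 h | Section 4 | SAP |
|---|---|---|
| Doxycycline, rectal vs vaginal biopsy | Primary | Not tested |
| Doxycycline, rectal vs cervical tissue | Not named | Primary |
| Doxycycline, plasma | Not named | Primary |
| Doxycycline, rectal vs vaginal swab | Not named | Primary |
| Bictegravir, rectal vs vaginal biopsy | Secondary | Not tested |
| Bictegravir, rectal vs cervical tissue | Not named | Exploratory |
| Bictegravir, plasma and swab | Not named | Exploratory |

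Primary tests go from one to three, and secondary endpoints from one to none. No SAP primary test matches the Section 4 endpoint exactly, because the only tissue test uses cervical rather than vaginal samples.

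**Size of the error-rate effect**

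The plan gives no power statement, effect size or standard deviation, so it has no figure of its own to reproduce.

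Inputs from the documents: three primary tests, a threshold of 0.05 for each, and 10 women and 10 MSM. Assumptions: two-sided tests (the SAP does not say), all samples evaluable, no ties.

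1. Nominal size 0.05 per test.
   - Independent tests: 1 − 0.95³ = 0.1426, or 14.3%.
   - Upper bound under any dependence: 3 × 0.05 = 0.15.
   - Fully dependent tests: 0.05.

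2. Exact size of the Wilcoxon rank-sum test at 10 vs 10. P falls below 0.05 when the smaller U is 23 or less, which has null probability 0.0433.
   - Independent tests: 1 − (1 − 0.0433)³ = 0.124.
   - Upper bound: 3 × 0.0433 = 0.130.
   - Fully dependent tests: 0.043.

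3. Correlated measures. Plasma, swab and tissue values come from the same people after the same dose, so independence is doubtful. A simulation of 40,000 trials, with normal data and an equal assumed correlation between the three measures, gave:

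| Assumed correlation | At least one false positive |
|---|---|
| 0 | 12.5% |
| 0.3 | 12.1% |
| 0.5 | 11.1% |
| 0.8 | 9.3% |

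The result at zero correlation agrees with the exact 12.4%. The documents give no correlations, so these values only show a range.

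4. Comparators. A single primary test has 5% nominal and 4.3% exact error. Three primaries under Bonferroni use 0.05 / 3 = 0.0167 each. The exact size per test is then 0.0147 (U of 18 or less), and the family-wise error is at most 3 × 0.0147 = 0.044.

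**The case against.** The strongest case against pressing this is about scale. The trial is a 20-person, single-dose pharmacology study with no efficacy claim, success criterion or power statement. A difference in concentration between sites or sexes is not a success in either direction. That stands: the main harm is ambiguity and room for selective reporting, and a reader who inferred a false confirmatory claim would go beyond the documents.

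Four other stronger readings are tempting, and the documents do not support them:

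- A reader might infer that the promised bictegravir result will never appear. The SAP still compares bictegravir in tissue at 24 hours, with the same test and the same 0.05 threshold as doxycycline. What is lost is its declared rank, and the match to vaginal tissue.
- A reader might infer that the study summary also restricts both objectives to biopsies. Its objectives speak of tissue pharmacology. The summary describes measurement in rectal and vaginal regions and includes collection of secretions, so swabs could arguably fit. The restriction to biopsies comes from Section 4. The objection to plasma is stronger than the objection to swabs.
- A reader might infer that new labels alone would bring the SAP into line. They would not, because the SAP has no vaginal-tissue comparison for either drug.
- A reader might take 5% to 15% as the exact error range. Those are nominal limits. With the exact Wilcoxon size and complete data the range is 4.3% to 13.0%.

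It is also fair to say that the documents give Section 4 no precedence over the SAP. Amending Section 4 would resolve the conflict equally well if alpha were controlled.

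**Conclusion.** The contradiction is real, and nothing elsewhere in the documents resolves it. Followed as written, the SAP allows a primary finding from plasma or swabs, which Section 4 does not name, and tests bictegravir in tissue below its declared rank.

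The chance of at least one false-positive primary result is 14.3% nominal if the tests are independent (at most 15%). With the exact test it is 12.4% if independent (at most 13.0%), and about 9% to 12% at assumed correlations of 0.3 to 0.8. A single test has 5% nominal and 4.3% exact. The exact figures assume two-sided tests, 10 evaluable participants per group and no ties.

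The text comparison alone supports the conclusion; the error rates only size it. The point should be corrected before analysis, but it does not put the trial's conduct in question.

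**What to change.** Before any data are analysed:

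1. Name one primary comparison by drug, tissue and time, in identical terms in Section 4 and the SAP: doxycycline in biopsies at 24 hours.
2. Reconcile vaginal (Section 4) with cervical (SAP) tissue for both drugs. Section 6 already plans both kinds of biopsy at Visit 6, so no new samples are needed.
3. Add a Secondary Outcome heading to the SAP for the same biopsy comparison of bictegravir.
4. Label the plasma and swab comparisons, and all TAF and FTC comparisons, as supportive or exploratory.

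If the sponsor prefers three primary doxycycline tests, Section 4 should list all three and alpha should be controlled, for example by Bonferroni at 0.0167 per test.

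The cost is an edit to Section 4 and two SAP paragraphs, plus possibly a small change to the tissue analysis. The downside is that plasma and swab P-values can no longer be reported as unadjusted primary results.

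### Section 4 sets the primary (doxycycline) and secondary (bictegravir) endpoints in rectal and vaginal biopsies, but the SAP's only tissue tests compare rectal with cervical tissue

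*Combined protocol and SAP*

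**What the plan says.** Section 4 (Study Endpoints) gives the primary endpoint as "to compare doxycycline concentrations in rectal and vaginal biopsies collected 24 hours after a single dose" and the secondary endpoint as "The comparison of bictegravir concentrations in rectal and vaginal biopsies collected 24 hours after a single dose". The study summary is in line with this. Its secondary objective is "To determine the tissue pharmacology of single dose bictegravir for HIV PEP", and its design paragraph speaks of measuring drug "concentrations in the rectum and vaginal regions".

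The Statistical Analysis Plan in Section 18 lists three comparisons at 24 hours under its primary outcomes: plasma doxycycline in men and women, a swab test ("Median rectal and vaginal swab doxycycline concentrations collected at 24 hours after dosing will be compared using a Wilcoxon test") and a tissue test ("Median rectal and cervical tissues doxycycline concentrations collected at 24 hours after dosing will be compared using a Wilcoxon test"). The same three follow for the antiretrovirals under the heading "Exploratory Outcomes: Comparison of TAF, FTC, and BIC concentrations in blood and tissue between men and women". The tissue test there reads "Median rectal and cervical tissue TAF, FTC, and BIC concentrations collected at 24 hours after dosing will be compared using a Wilcoxon test".

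Section 6 (Visit 6) assigns the biopsy by anatomy. Participants with a vagina have the vaginal and cervical procedure, with 1 to 2 specimens from each site and an optional rectal biopsy. Everyone else has a rectal biopsy. Section 15 caps the genital tract samples at two vaginal and two cervical.

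**The concern.** The endpoint section and the analysis section name different tissues for the comparison that the study exists to make. The primary objective is the tissue pharmacology of single-dose doxycycline, so the tissue test is the one that answers it. If the SAP is followed to the letter, the report will contain a rectal versus cervical result and no test of the primary endpoint as Section 4 words it. If the team instead goes back to Section 4 when writing up, it must choose between two genital tract tissues, possibly with the concentrations already in view. In either case the report could not plainly say that the stated endpoint was analysed as planned.

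**Working it through.** No arithmetic beyond counting applies. The SAP reports no power or effect size for these tests, so there is no figure of the plan's own to reproduce. The check sets Section 4 against every test in the SAP.

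| Comparison at 24 h | Role in Section 4 | SAP tests, doxycycline | SAP tests, bictegravir |
|---|---|---|---|
| Plasma, men vs women | none | 1 | 1 |
| Rectal vs vaginal swab | none | 1 | 1 |
| Rectal vs vaginal biopsy | primary (doxycycline), secondary (bictegravir) | 0 | 0 |
| Rectal vs cervical biopsy | none | 1 | 1 |

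1. *Count.* Four drugs (doxycycline, TAF, FTC, bictegravir) × 3 comparisons = 12 listed tests. Four of these are tissue tests, one per drug, and all four use cervical tissue. Two of the four concern a Section 4 endpoint: 0 of 2 use vaginal biopsy tissue and 2 of 2 use cervical tissue.

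2. *Are the two tissues interchangeable in this protocol?* No. Visit 6 in Section 6 and the risk text in Section 15 each give separate numbers for vaginal and cervical specimens, and inclusion criterion 9 names both.

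3. *Does the swab test fill the gap?* No. Visit 6 says that the swabs taken through the scope or speculum are for secretions. Section 4 specifies biopsies, and the SAP itself lists swab and tissue as different comparisons.

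4. *Which doxycycline test is primary?* Section 4 has one primary endpoint. The SAP puts three doxycycline tests (plasma, swab, tissue) under its primary heading and does not rank them.

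5. *Which tier holds bictegravir?* It is secondary in the study summary and Section 4, and exploratory in the SAP. This changes a label but no stated test or threshold.

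6. *Who is in each group?* The SAP's heading describes a comparison of men with women. The study population includes trans women, and biopsy type at Visit 6 depends on whether the participant has a vagina, so the tissue groups need not coincide with men and women. The optional rectal biopsy means that one person can supply both tissues. The SAP says only Wilcoxon, without stating the paired or unpaired form.

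**The case against.** The best defence is that vaginal is used loosely. Visit 6 calls the combined procedure the vaginal biopsy, and both the compensation list in Section 17 and Table 1 refer only to rectal and vaginal biopsy. Section 4 may do the same, in which case cervical tissue falls within the endpoint and the SAP simply picks it. The SAP, followed as written, is also unambiguous. This reading is plausible and it lowers the severity. It does not remove the point: the SAP would then test one of two sampled tissues without giving a reason or a role for the other.

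A reader might infer three stronger things that the documents do not support:

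- *The primary endpoint certainly goes untested.* That holds only on the strict reading of vaginal.
- *The plan lets the team pick a tissue after seeing results.* The SAP fixes cervical tissue. A choice arises only if the team turns to Section 4 instead.
- *Cervical sampling is unspecified, because the biopsy procedure text in Section 6 describes only vaginal specimens.* Visit 6 and Section 15 both give the cervical number. Only the cervical specimen thickness is missing.

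It is also fair to say that the study is small (20 participants), and that the documents attach no decision rule or power claim to this test.

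**Conclusion.** The mismatch is real and nothing else in the documents repairs it. On the strict reading, neither Section 4 endpoint has a matching SAP test (0 of 2). On the shorthand reading, each is tested in one of the two sampled genital tract tissues, without a reason. The documents do not settle which reading was meant. The point should be fixed, but it does not invalidate the study: the specimens for either comparison are already planned at Visit 6, and the remedy can be wording alone. No effect on a result can be calculated from the documents. The unranked doxycycline tests and the bictegravir label are lesser inconsistencies that belong in the same edit.

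**What to change.** Before any concentrations are examined, make Section 4 and the SAP name the same tissue, in one of three ways:

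- If Section 4 stands, add rectal versus vaginal biopsy tests for doxycycline (primary) and bictegravir (secondary), and keep the cervical tests as supporting. The listed tests go from 12 to 12 + 2 = 14.
- If cervical tissue was intended, amend Section 4.
- If both were intended, name both and say which is primary.

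In the same edit:

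- State which of the plasma, swab and tissue doxycycline tests is the primary one, and give the others a supporting role.
- List bictegravir as secondary in the SAP.
- Label the tissue test as a comparison by tissue rather than by sex, and specify an unpaired rank-sum test with one tissue per participant. Optional rectal biopsies from participants who gave genital tract biopsies then stay out of that test.
- State that a cervical test includes only participants who gave a cervical sample. The eligibility criteria do not require a cervix, so this group may be smaller than the group with a vaginal sample.

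Cost: wording only, if Section 4 is amended to cervical tissue. If vaginal tissue is to be tested, it must be assayed separately from cervical tissue, which the protocol does not say will be done, and one comparison is added per drug. No new procedure or visit is needed.
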